4. DATA MANAGEMENT

4.1 DATA COLLECTION

All study information will be collected electronically using password-protected tablets, with direct entry into the Research Electronic Data Capture (**REDCap**) database. REDCap is a validated software system, compliant with ICH-GCP and regulatory requirements and can support online and offline data capture.

4.2 DATA MANAGEMENT AND STORAGE

The management of study records will prioritize confidentiality, integrity, and security of data. Access to the REDCap database will be restricted to authorized study team members, using individual password-protected accounts with role-based permissions. Audit trails will automatically document data entry, modifications, and access.

To protect participant confidentiality:

- All case report forms (CRFs) will be anonymized using the study identification code.
- Laboratory samples will be labelled with unique barcodes linked to the participant's study identification code but not to personal identifiers.
- Datasets will be de-identified prior to analysis, ensuring that no directly identifying information is used in reports or publications.
- Personally identifiable information (including names, identify numbers, address, geolocation data, telephone numbers) will be stored in a separate table in the database with restricted access and identified by a separate identifier. This information will not be included on the data repository. If access to this data is required for research purposes, including for linkage to health system data (NHLs or Tier.net) it will be made available on a secured data enclave that restricts download or copying of data.

Data will be stored on secure, access-controlled servers with routine back-up procedures in place. Hard-copy study records, where required, will be kept in locked cabinets in restricted-access areas. Data management procedures will comply with institutional policies, Good Clinical Practice (GCP) standards, and relevant national data protection regulations.

4.3 PUBLICATION & DATA SHARING POLICY

Study findings will first be shared with local stakeholders and the Department of Health. Results will subsequently be disseminated through peer-reviewed publications and presentations at scientific meetings in the form of posters and oral communications. All proposed publications and presentations, including manuscripts, conference abstracts, oral presentations and posters, that include ATTIS data will be submitted to the ATTIS Scientific and Management Steering Committee for review in the form of a written proposal. Each proposal will outline the objectives, data required, proposed analyses and plans for publication or presentation. Once initial approval is granted, we will share the draft manuscript or presentation, including the proposed author list, citations of ATTIS datasets and acknowledgments with the Steering Committee for final review and approval prior to external submission.

Final peer-reviewed manuscripts will be submitted to open-access journals indexed on PubMed to ensure wide accessibility of the study outputs. In line with data-sharing principles, de-identified datasets and associated metadata will be made available to qualified researchers upon reasonable request, subject to approval by the ATTIS Scientific and Management Steering Committee and in compliance with data protection regulations.

5. STATISTICAL CONSIDERATIONS AND MODELLING

5.1 SAMPLE SIZE CALCULATIONS

CORE STUDY

The core study has two co-primary objectives: (1) to compare IGRA positivity in child household contacts of participants with aTB-C with that of community controls; (2) to compare IGRA positivity in child household contacts of participants with aTB-C cases with that of participants with sTB-c. We are using child IGRA positivity as a proxy measure of TB transmission.

Based on our existing data on the prevalence of aTB-C in each setting, we expect to screen 60,000 individuals in Bandung and 30,000 in KwaZulu Natal to identify 150 cases of aTB (**Table 3**). We expect ~20% of children to be IGRA positive in control households in Bandung and 7% to be positive in KwaZulu Natal, and an average of 1.5 (SD=0.7) and 2.5 (SD=1.6) children per household, respectively, in each setting. We have assumed an intra-cluster correlation coefficient (ICC) of 0.20-0.30 in each setting, based on our data in KwaZulu Natal⁶⁴.

Table 3: Assumptions used to determine overall scale of screening and power for the asymptomatic TB transmission in Indonesia and South Africa study

Parameter	Indonesia	South Africa
Number screened	60,000	30,000
Asymptomatic TB prevalence (Clinical -, CXR positive, micro +/-)	0.25%	0.50%
Number of asymptomatic TB cases detected	150	150
Number of control HH	300	300

IGRA positivity in children aged 2-14 years	STB index HH: 40% Control HH: 20%	STB index HH: 18% Control HH: 7%
Household size (children aged 2-14 years)	Mean = 1.5 SD = 0.7	Mean = 2.5 SD = 1.6
Intra cluster correlation (ICC)	0.20 to 0.30	0.20 to 0.30

For our first co-primary objective, we have used the absolute risk difference in child IGRA positivity (rather than the risk ratio) as our effect estimate of interest, because of the difference in duration of exposure (lifetime exposure to community transmission for children in control households, vs a relatively short duration of exposure to the index case for children in aTB-C households).

If the true risk difference between IGRA positivity in aTB-C households compared to control households is 10-15%, inclusion of 150 aTB-C households and 300 control households will provide $\geq 90\%$ power to detect a significant difference in household IGRA positivity between these groups. We will have 80% power to detect a minimum difference of 12% in Bandung and 7% in KwaZulu Natal ([Table 4](#)).

Table 4: Minimum risk difference that can be detected in each site with 80% power, comparing aTB and control households

Number aTB cases	Number controls ¹	Mean children per HH	ICC	% IGRA positive in control HH	% IGRA positive in aTB HH	Risk difference ²	Power
Indonesia							
150	300	1.5	0.30	20%	32%	12%	80%
South Africa							
150	300	2.5	0.30	7%	14%	7%	80%

¹Number of control households. ²Absolute difference = proportion of children IGRA+ in aTB households minus proportion of children IGRA+ in control.

For our second co-primary objective, we have used the risk ratio (relative risk) as the effect estimate of interest, because the duration of exposure for children in aTB-C and sTB-C households is expected to be similar. For policy decisions, it would be useful to know that the transmission risk of aTB-C is not substantially lower than that of sTB-C; therefore, we have used a non-inferiority approach for our power calculations. We have assumed that the prevalence of IGRA positivity in children in sTB-C households is 40% in Bandung and 18% in KwaZulu Natal (our best estimates, based on available data). With 150 sTB-C and 150 aTB-C index cases, we will have at least 80% power in each setting to demonstrate that the transmission risk with aTB-C is not less than 50% compared with that of sTB-C, assuming that the true risk ratio (RR) is at least 0.90 ([Table 5](#)).

Table 5: Relative reduction that can be excluded with 80% power, comparing aTB and sTB households¹

Number sTB cases	Number aTB cases	% IGRA positive in sTB HH	% IGRA positive in aTB HH	Risk ratio (aTB/sTB)	Relative reduction that can be excluded ²
Indonesia - aTB vs sTB					
150	150	40%	28%	0.70	0.46
150	150	40%	32%	0.80	0.55
150	150	40%	36%	0.90	0.63
South Africa - aTB vs sTB					
150	150	18%	12.6%	0.70	0.43
150	150	18%	14.4%	0.80	0.49
150	150	18%	16.2%	0.90	0.55

¹Assuming ICC=0.30. ²Lower limit of 95% confidence interval for risk ratio

CASE-CONTROL STUDY (SUB-STUDY 1)

The case-control study will enrol 150 aTB-C and 150 sTB-C cases, and 300 community controls with no TB. Assuming that the true sensitivity and specificity of the Plus Life tongue swab and bioaerosol collection facemask diagnostic tools are between 70-95%, with 150 aTB-C and 150 sTB-C cases, we will be able to estimate the sensitivity with a precision of $\pm 7.6\%$ to $\pm 4.0\%$. With 300 controls, we will be able to estimate the specificity with a precision of $\pm 5.3\%$ to $\pm 2.6\%$.

TB-UNCONFIRMED (TB-U) COHORT STUDY (SUB-STUDY 2)

A total of 1000 individuals (500 from Bandung and 500 from KwaZulu Natal) identified through the community-based screening who have chest x-rays suggestive of TB and negative baseline sputum will be followed prospectively. Based on published data that found that individuals with radiographic evidence of TB progressed to microbiologically-positive disease at an annualized rate of 10% (95% CI 6.2-13.3)⁶⁵, we anticipate 31-66 progressors to microbiologically-confirmed TB from each site.

With 50 individuals who progress and 100 who do not, we will have $\geq 80\%$ power to detect a difference of 0.50 standard deviations in mean biomarker concentrations between the two groups. If the prevalence of biomarkers in individuals who do not progress is 10-20%, we would have $\geq 80\%$ power to detect an increase to 30-40%.

STAGE GATE

We have used our best estimates of the prevalence of TB-C, prevalence of IGRA positivity, number of children per household, and value of the ICC to inform our sample size calculations, based on the available data in each setting. However, given the limited data available, there is uncertainty in these assumptions and a small change in any one of these (e.g. in household size, ICC, or the prevalence of

IGRA positivity) can have a large impact on our power. Therefore, after 20% of the population has been screened at each site (12,000 in Bandung and 6000 in KwaZulu Natal), we will assess the accuracy of the key assumptions used in our sample size calculations. Specifically, we will analyse the available data to determine the population prevalence of aTB-C, the proportion of children aged 2-14 years who are IGRA positive, average household size, and the estimated ICC. We will then use these revised estimates to further refine our power calculations for the co-primary endpoints. The results will be discussed with the funders and, if necessary, we may adjust the project sample size, budget and timelines to ensure sufficient power to address both co-primary endpoints. We will also evaluate any data available for the TB-U cohort (proportion of participants meeting the screening definition of TB-U who are confirmed aTB-C by 2 additional sputum specimens, proportion of TB-U participants who progress to TB-C) and we may adjust the TB-U cohort size to address its powering endpoint.

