Sample size	
Community-based TB screening: 90,000 (60,000 in Bandung and 30,000 in KwaZulu Natal)
 
IGRA assessments in children: 2,400 (900 in Bandung and 1500 in KwaZulu Natal)
 
Case-control phenotyping study: 1,200 (600 in each setting)
 
Cohort study: 1,000 (500 in each setting)
 
We estimate that we will need to screen 60,000 adolescents/adults in Bandung and 30,000 adolescents/adults in KwaZulu-Natal to identify 150 cases with aTB-C in each setting. Mtb infection status in child HHC will be measured in 600 households in each setting (150 aTB-C cases, 150 sTB-C cases, 300 controls). The estimated average number of children aged 2-14 years per household is 1.5 in Bandung and 2.5 in KwaZulu-Natal. Therefore, we will enrol approximately 900 children in Bandung and 1,500 children in KwaZulu-Natal for IGRA assessments. Once 20% of the community has been screened in each setting, an interim analysis will be conducted to assess assumptions and inform final sample size calculations.
 
In the cross-sectional study of household Mtb infection (core study), 150 index cases with aTB-C and 300 community controls (1:2 ratio) will provide $\geq 80\%$ power to detect a difference between the IGRA positivity of child household contacts of adults with aTB-C and community controls if the true risk difference is 10-15%. Assuming that the true risk ratio comparing child

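### Section 5.1 claims at least 90% power for a 10-15% risk difference, but Bandung has only about 70-78% at 10%, and Table 4 gives 80% at 12%

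*Protocol*

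**What the plan says.** The protocol gives the power for the first co-primary objective in three places, always with 150 aTB-C and 300 control households.

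- **Section 5.1, Core study:** "If the true risk difference between IGRA positivity in aTB-C households compared to control households is 10-15%, inclusion of 150 aTB-C households", and then "300 control households will provide $\geq 90\%$ power to detect a significant difference in household IGRA positivity between these groups". The sentence is not limited to one site.
- **Section 5.1, next sentence, and Table 4:** "We will have 80% power to detect a minimum difference of 12% in Bandung and 7% in KwaZulu Natal". The Bandung row of Table 4 is 20% against 32%, ICC 0.30, power 80%. The KwaZulu-Natal row is 7% against 14%, ICC 0.30, power 80%.
- **Protocol summary, Sample size:** the same households "will provide $\geq 80\%$ power to detect a difference between the IGRA positivity of child household contacts" in the two groups, again over a range of 10-15%.

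The summary makes clear that these household numbers apply to each setting, and section 5.2 analyses every endpoint separately by setting.

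**The concern.** Power rises with the size of the true difference. If 12% is the smallest difference with 80% power in Bandung, then 12% cannot also have at least 90%, and 10% must have less than 80%. The section 5.1 sentence therefore conflicts with the sentence after it over the lower part of its own range. The summary's 80% fails at 10% in Bandung for the same reason.

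This is the stated power of a co-primary comparison. A reader who takes section 5.1 at its word would expect at most a 10% chance of missing a true 10-point difference in Bandung. The protocol's own inputs put that chance at about 22-30%. The Stage gate part of section 5.1 sets out to refine these power calculations and possibly change sample size, budget and timelines, so it needs one coherent starting figure.

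**Working it through.** **Inputs (section 5.1, Tables 3 and 4)**

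- 150 aTB-C and 300 control households per setting.
- Control positivity: "We expect ~20% of children to be IGRA positive in control households in Bandung and 7% to be positive in KwaZulu Natal".
- Household size: "an average of 1.5 (SD=0.7) and 2.5 (SD=1.6) children per household".
- ICC 0.20-0.30; Table 4 uses 0.30.
- Alpha is not stated for this objective. Two-sided 5% is assumed.

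Children in Bandung: 150 × 1.5 = 225 (aTB-C) and 300 × 1.5 = 450 (control). In KwaZulu-Natal: 375 and 750.

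**Formulas**

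- Design effect, equal household sizes: DE = 1 + (m − 1) × ICC.
- Design effect, unequal sizes: DE = 1 + ((1 + CV²) × m − 1) × ICC, with CV = SD/m.
- Unpooled variance: SE² = DE × [p1(1 − p1)/n1 + p0(1 − p0)/n0], and power = Φ(RD/SE − 1.96).
- The pooled version uses the pooled proportion for the null standard error.

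Bandung design effects are 1.10 (ICC 0.20) and 1.15 (ICC 0.30) with equal sizes, and 1.165 and 1.248 with SD 0.7.

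**Step 1: the plan's own figure, Bandung at 12%.** With ICC 0.30, direct calculation gives 84.0% (unpooled, unequal sizes) to 88.4% (pooled, equal sizes). Table 4's 80% is therefore not reproduced exactly and looks slightly conservative. Two settings come close to it: two-sided alpha 0.025 with unequal sizes (78.9%), or one child per household at two-sided 5% (79.2%). Those two settings give 63.2% and 65.1% at a 10% difference.

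**Step 2: Bandung at 10% (20% against 30%), least favourable case.** ICC 0.30, unequal sizes, unpooled:

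SE² = 1.248 × (0.30 × 0.70/225 + 0.20 × 0.80/450) = 1.248 × 0.0012889 = 0.0016085, so SE = 0.0401.

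RD/SE = 2.493, and power = Φ(2.493 − 1.96) = 70.3%.

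**Step 3: Bandung at 10%, all variants**

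| ICC | Household sizes | DE | Unpooled | Pooled |
|---|---|---|---|---|
| 0.20 | equal | 1.10 | 75.7% | 77.9% |
| 0.20 | unequal | 1.165 | 73.2% | 75.6% |
| 0.30 | equal | 1.15 | 73.8% | 76.2% |
| 0.30 | unequal | 1.248 | 70.3% | 72.8% |
| none | – | 1.00 | 79.5% | 81.6% |

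A simulation with beta-binomial households, sizes of mean 1.5 and SD 0.7, a cluster-robust Wald test and 8,000 runs gave 70.7% (ICC 0.30) and 73.7% (ICC 0.20). Even a one-sided 5% test with no clustering reaches only 88.6%. No variant reaches 90%.

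**Step 4: where Bandung reaches the stated levels.** Across the ICC 0.20-0.30 variants, 80% is reached at a difference of about 10.3-11.3% and 90% at about 12.1-13.3%. At 15% power is 95-98%.

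**Step 5: scaling from Table 4 alone.** 80% power at 12% means RD/SE = 1.96 + 0.84 = 2.80. With SE held fixed, power at 10% is Φ(2.80 × 10/12 − 1.96) = 65%, and 90% needs 12 × (1.96 + 1.28)/2.80 = 13.9%.

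**Step 6: KwaZulu-Natal.** The same variants give 94-99% at 10% and above 99% at 15%. At 7% they give 74-90%, a range that contains Table 4's 80%. 90% is reached at about 7.1-9.1%.

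**The case against.** Several points on the other side are fair.

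- At least 90% implies at least 80%, so section 5.1 and the summary differ without contradicting each other logically. That stands. The real conflict is between each of them and Table 4, for Bandung.
- The 90% figure drives no rule. The stage gate re-estimates prevalence, positivity, household size and ICC and recomputes power from them. That stands too: the figure is only the baseline against which the recalculation will be read.
- The correct direction is visible in the adjacent sentence. It is, but a reader should not have to choose between two adjacent statements, and the summary carries no such correction.
- If the true aTB/sTB risk ratio is 0.90, as assumed for the second objective, Bandung would have 36% against 20%, a difference of 16% with 97-99% power. This makes a 10% difference less central, but section 5.1 itself names 10-15% as the range and claims power over all of it. A 10% difference corresponds to a risk ratio of 0.75 (30%/40%), inside the 0.70-0.90 range of Table 5.
- Exact replacement figures depend on alpha, the variance formula, the handling of household size and the matched-set random effect in section 5.2, which these formulas leave out. This is right, and it is why the final figures should come from the sponsor's own stated method.

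None of these makes at least 90% true at 10% in Bandung.

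**Conclusion.** The concern holds. As written, the power statement for the first co-primary objective is wrong for Bandung over the lower part of its range. At a 10% difference power is about 70-78%, or about 65% if Table 4 is taken at face value. Neither the 90% in section 5.1 nor the 80% in the summary is met there under the protocol's ICC range. The statement is right for KwaZulu-Natal throughout and for Bandung from about 12-13% by direct calculation (about 14% on Table 4's scaling).

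The inconsistency with Table 4 needs no assumption. The percentages rest on two-sided 5%, ICC 0.20-0.30, the stated household sizes and separate analysis by setting. The design and household numbers are not themselves in error.

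**What to change.** Replace the single 10-15% claim by one power statement per site, and use the same figures in the summary, section 5.1 and Table 4. State the alpha, the ICC, how variable household size enters, and the method, then rerun both sites on that one basis.

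At two-sided 5% and ICC 0.20-0.30, the figures to expect are roughly:

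- **Bandung:** 70-78% at 10%, 80% from about 10.3-11.3%, 90% from about 12.1-13.3%.
- **KwaZulu-Natal:** 74-90% at 7%, 90% from about 7.1-9.1%, 94-99% at 10%.

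If the sponsor keeps Table 4's more conservative 12% for Bandung, the text should follow it: about 65% at 10%, and 90% only from about 14%. Figures from the two bases should not be mixed.

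The cost is wording and one rerun of the calculation. No design change is required, but the stated power for Bandung becomes less favourable.

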5.2 ANALYTICAL APPROACH

Descriptive statistics will be used to summarise participant characteristics separately for each study setting, including household-level characteristics (e.g. socioeconomic status, household construction, number of household members), index-case level characteristics (e.g. age, sex) and child-level characteristics. The analyses for each endpoint will be conducted separately for each setting.

CORE STUDY

Comparison of aTB and control households: For the primary analysis, we will use random-effects logistic regression with a fixed effect for exposure group (aTB vs control) and a random intercept for household. Since control houses will be selected from the same neighbourhood as the aTB index cases, we will also include a random effect for matched set. From the fitted model, we will estimate the marginal risk difference in the proportion IGRA positive between the two groups.

Matching on neighbourhood will provide some control of confounding by neighbourhood-level factors (e.g. socioeconomic status, background exposure in the community). However, we will also conduct multivariable analyses, explicitly controlling for confounding using child-level (e.g. age, sex and degree of contact with index, such as sleeping in same room etc) and household-level covariates (e.g. household crowding). Covariate adjustment will be guided by theoretical causal diagrams, defined *a priori*.

Comparison of aTB and sTB households: For the primary analysis, we will use random-effects logistic regression with a fixed effect for TB exposure group (aTB vs sTB) and a random intercept for household. The marginal risk ratio will be estimated from the fitted model.

We will also conduct multivariable analyses, controlling for confounding using child-level, index case-level (age, sex, HIV status) and household-level covariates, as described above, with covariate adjustment guided by theoretical causal diagrams, defined *a priori*. If there is evidence of a difference in the infectiousness of aTB compared with sTB we will explore whether this is mediated through characteristics of index case disease severity (bacillary burden, cavitation etc) or other mechanisms.

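### At two-sided 5% with no loss, Table 4's 12 points for Bandung has about 84–88% power, not 80%; the protocol states no alpha or loss that would explain the figure

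*Protocol*

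**What the plan says.** Section 5.1 of the protocol bases power for the comparison of aTB-C with control households on the absolute risk difference. It assumes "inclusion of 150 aTB-C households and 300 control households" in each setting. On the control rate: "We expect ~20% of children to be IGRA positive in control households in Bandung and 7% to be positive in KwaZulu Natal". On household size: "an average of 1.5 (SD=0.7) and 2.5 (SD=1.6) children per household". It takes an "intra-cluster correlation coefficient (ICC) of 0.20-0.30 in each setting", and both rows of Table 4 use 0.30.

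Table 4 is titled "Minimum risk difference that can be detected in each site with 80% power, comparing aTB and control households". It gives 20% against 32% (12 points) for Indonesia and 7% against 14% (7 points) for South Africa, each with power 80%. The text repeats this: "We will have 80% power to detect a minimum difference of 12% in Bandung and 7% in KwaZulu Natal". The sentence just before it promises at least 90% power if the true difference is 10–15%, without naming a site. The Protocol Summary gives at least 80% for the same 10–15% range.

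For Table 4 the protocol states no significance level, no variance formula and no household loss, and it does not say whether the household-size SD was used. The planned analysis in Section 5.2 is "random-effects logistic regression with a fixed effect for exposure group (aTB vs control) and a random intercept for household", with a further random effect for matched set.

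**The concern.** Table 4 prints nearly everything needed to recompute its own result, and at the conventional level the Bandung row does not come out at 80%. The method that returns the KZN row gives a smaller minimum difference for Bandung than the table shows.

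The adjacent sentence adds a second difficulty. Twelve points lies inside 10–15 points, so Bandung cannot have both 80% and at least 90% power at 12.

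What is at stake is a reproducible baseline. The Stage Gate paragraph of Section 5.1 says power will be recalculated after 20% of screening, and that size, budget and timelines may then change. If the method behind the first calculation is unknown, a changed result cannot be attributed to new data rather than to a different method.

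**Working it through.** **Inputs** (Section 5.1, Tables 3 and 4). Households 150 and 300. Mean children m = 1.5 (SD 0.7) in Bandung and 2.5 (SD 1.6) in KZN. ICC ρ = 0.30, taken on the proportion scale. Rates 20% against 32%, and 7% against 14%. Assumed because not stated: two-sided alpha 0.05, no loss, no continuity correction.

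**Design effect (DE).**
- Equal sizes, 1 + (m − 1)ρ: Bandung 1 + 0.5 × 0.30 = 1.15; KZN 1 + 1.5 × 0.30 = 1.45.
- Unequal sizes, 1 + ((1 + CV²)m − 1)ρ: Bandung CV = 0.7/1.5 = 0.467, DE = 1.248; KZN CV = 1.6/2.5 = 0.64, DE = 1.757.

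**Effective children per group** (households × m / DE).
- Bandung: 225/1.15 = 195.7 and 450/1.15 = 391.3; with size variation 180.3 and 360.6.
- KZN: 375/1.45 = 258.6 and 750/1.45 = 517.2; with size variation 213.4 and 426.8.

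**Power** = Φ[(Δ − z·SE0)/SE1]. SE1 uses the two separate proportions. SE0 uses the pooled proportion, or equals SE1 in the unpooled version.

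The KZN row first, pooled with size variation. The pooled proportion is (0.14 + 2 × 0.07)/3 = 0.0933, SE0 = 0.02439 and SE1 = 0.02677. (0.07 − 1.96 × 0.02439)/0.02677 = 0.83, so power is 79.7%, and 80% is reached at 7.04 points. The row is reproduced.

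The same method for Bandung. The pooled proportion is 0.24, SE0 = 0.03896 and SE1 = 0.04063. (0.12 − 1.96 × 0.03896)/0.04063 = 1.07, so power is 85.9%, and 80% is reached at 11.0 points.

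All four variants at two-sided 5%, no loss:

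| Method | Bandung power at 12 points | Bandung 80% point | KZN power at 7 points | KZN 80% point |
|---|---|---|---|---|
| Equal sizes, pooled | 88.4% | 10.5 | 86.3% | 6.3 |
| Equal sizes, unpooled | 86.8% | 10.9 | 82.1% | 6.8 |
| With size SD, pooled | 85.9% | 11.0 | 79.7% | 7.0 |
| With size SD, unpooled | 84.0% | 11.3 | 74.4% | 7.6 |

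Adding a continuity correction to the last row brings Bandung to 81.4% (11.8 points) but takes KZN down to 70.0%.

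Simulation of a random-intercept logistic model with varying household size (600 runs, likelihood-ratio test, standard error about 1.6 percentage points) gives 86.7% for Bandung and 85.7% for KZN at 5%.

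**What would give both rows.** Pooled, equal sizes:
- Two-sided 0.025, no loss: Bandung 82.3% (80% at 11.6 points), KZN 79.9% (7.0 points).
- Two-sided 0.05, 20% of households lost: Bandung 80.9% (11.9 points), KZN 78.5% (7.2 points).

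The simulated model at 0.025 gives 79.8% and 79.3%.

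**Cross-check against Table 5.** Its footnote names a 95% confidence interval, and it uses the same 150 aTB households and ICC 0.30. The limit excluded with 80% power is RR × exp[−(z + 0.84)·SE(log RR)], where SE² = (1 − p1)/(n·p1) + (1 − p2)/(n·p2) and n = 195.7 per group for Bandung, equal sizes.

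| Setting | RR 0.70 | RR 0.80 | RR 0.90 |
|---|---|---|---|
| Table 5, Bandung | 0.46 | 0.55 | 0.63 |
| 5%, no loss | 0.47 | 0.55 | 0.63 |
| 0.025, no loss | 0.45 | 0.53 | 0.60 |
| 5%, 20% loss | 0.45 | 0.52 | 0.60 |

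The Bandung rows of Table 5 fit 5% with no loss. The KZN rows (0.43, 0.49, 0.55) fit none of these settings; 5% with no loss gives 0.39, 0.46 and 0.52, so they lend the two alternatives no support.

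**The 90% sentence.** By the same formula at 5% with no loss, Bandung has 70–76% power at 10 points, 84–88% at 12 and 95–97% at 15. KZN has 94–98% at 10 points. The sentence therefore holds for KZN over the whole range, but not for Bandung at 10 or 12 points.

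**The case against.** The strongest reply is that Table 4 names no alpha, so 5% is the reviewer's assumption. Splitting alpha across two co-primary objectives is an ordinary choice, and an allowance for household loss is equally common. Either one gives both rows by a single method, and the simulated random-intercept model at 0.025 lands almost exactly on 80% in both settings. This stands. A reader might infer that no single method can produce both rows, or that one row must be wrong; the documents do not support that, because they exclude neither assumption.

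What weakens the reply is that the protocol declares neither assumption for Table 4. The companion co-primary calculation names a 95% interval, and its Bandung figures fit no loss. If Table 4 used a stricter level or a loss allowance, it differs from Table 5 without saying so.

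A reader might also infer that the stage gate will use 12 and 7 points as thresholds. Section 5.1 says only that the inputs will be re-estimated and the power calculations refined, so Table 4 is not a decision rule.

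On the 90% sentence, the range could have been meant as 10 points for KZN and 15 for Bandung, where it would be true at 5%. The text does not say that.

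Detail on the test may sit in a statistical analysis plan that is not shown. That would supply the method, but would not remove the conflict between two power statements printed together in the protocol.

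**Conclusion.** The point holds in conditional form. At two-sided 5%, ICC 0.30 on the proportion scale, no loss and no continuity correction, 12 points in Bandung has about 84–88% power and 80% is reached at about 11 points (10.5–11.3). The row then understates power by 4–8 percentage points, or overstates the minimum difference by about 1 point. The KZN figure of 7 points has 74–86% depending on method and is reproduced by the pooled test with size variation.

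If alpha was 0.025, or about 20% household loss was built in, both rows are right to rounding and the defect is that this is not stated. Separately, at least 90% for 10–15 points and 80% at 12 points cannot both apply to Bandung.

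The discrepancy is conservative. It would be wrong to infer that 150 and 300 households are too few for the stated 12 points; nothing here puts the sample size in question. This is a minor correction.

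**What to change.** Recompute both rows of Table 4 by one method. Add a footnote giving alpha and sidedness, the variance method or model, whether the household-size SD is used, and any household loss.

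- If the basis is two-sided 5% with no loss, restate Bandung as 12 points with about 84–88% power (the single value for the chosen method), or as about 11 points at 80%.
- If a stricter alpha or a loss allowance was intended, keep 12 points, declare it, and explain why Table 5 uses a different basis or bring it into line.

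Then align the sentence in Section 5.1 on at least 90% power by naming the site and the difference it applies to. Check the Protocol Summary's statement of at least 80% over 10–15 points at the same time, since 10 points in Bandung gives 70–76% at 5% with no loss.

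The cost is one footnote, up to two table cells and one or two sentences. Sample size, design and analysis are unchanged.
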